### Treatment

Treatment will be administered on an outpatient basis. For ibrutinib a self-report pill diary will be utilized to report medication adherence. Reported AEs and potential risks are described in Section 8. Dose delays for ibrutinib and pembrolizumab are described in Section 5.1.6. No investigational or commercial agents or therapies other than those described below may be administered with the intent to treat the patient's malignancy. The starting dose of ibrutinib will be 420 mg daily, taken orally. The dose of pembrolizumab is fixed at 200 mg IV over 30 minutes every 3 weeks. Each cycle will last for 3 weeks.

Subjects will be enrolled in 3 + 3 design with 3-6 subjects per cohort to ensure a minimum of 3 and a maximum of 6 evaluable subjects per cohort. It is estimated that two cohorts will be needed during the dose escalation phase of the study as follows:

Dose Escalation Schedule		
Cohort	Dose	
	Ibrutinib	Pembrolizumab
0	420 mg PO qdaily	200 mg IV over 60 min q3wk
1	560 mg PO qdaily	200 mg IV over 60 min q3wk

Based on current available data, the ibrutinib starting dose will be 420 mg (Cohort 0). Ibrutinib dose could be escalated to 560 mg (Cohort +1) based on the safety and tolerability profile of the combination in Cohort 0. If DLT is seen with Cohort 0, the principal investigator will re-evaluate and discuss with Janssen and Merck on how to proceed.

Each subject will receive ibrutinib daily and pembrolizumab Q3W continuously and will undergo assessments for safety (DLTs, AEs, vital signs, clinical laboratory tests, ECOG performance status, and physical examinations) according to the schedule of assessments.

The DLT evaluation period will be defined as the time from the first dose of ibrutinib or pembrolizumab to 42 days (2 cycles) after the first dose or if a subject experiences a DLT within this time period. The total duration of dose interruptions for ibrutinib will be up to 6 days (intermittent or continuously), during a period of 42 days without a subject being deemed

inevaluable.

Rules for dose escalation and de-escalation are as follows:

1. A minimum of 3 evaluable subjects will be enrolled in each dose cohort. The administration of ibrutinib and pembrolizumab to the first and second subjects of each cohort will be separated by at least 72 hours. Providing there are no serious or unexplained safety issues, dosing of the remainder of the cohort will continue as suitable subjects are identified. All safety data will be reviewed before proceeding with an escalation or de-escalation decision.
2. A 3+3 dose-escalation design will be followed as summarized below:
  - If 0 out of the 3 evaluable subjects in a dose cohort experience a DLT during the DLT evaluation period, dose escalation may proceed to the next planned cohort.
  - If 1 of the 3 evaluable subjects in any dose cohort experiences a DLT during the DLT evaluation period, that dose cohort will be expanded to a total of 6 subjects. If no more than 1 of 6 subjects in the dose cohort experiences a DLT, dose escalation may proceed to the next planned dose cohort.
  - If 2 or more subjects in a dose cohort experience a DLT during the DLT evaluation period, the MTD will have been exceeded and no further subjects will be enrolled into that dose cohort.

There will be no intra-subject dose escalations.

### **5.1.1 Rationale for Flat Dose Regimen of Pembrolizumab**

An open-label Phase I trial was conducted to evaluate the safety and clinical activity of single agent pembrolizumab. The dose escalation portion of this trial evaluated three dose levels, 1 mg/kg, 3 mg/kg, and 10 mg/kg, administered every 2 weeks (Q2W) in subjects with advanced solid tumors. All three dose levels were well tolerated and no dose-limiting toxicities were observed. No MTD has been identified to date. In pharmacokinetic studies, the relationship between clearance and body weight is within the range observed for other antibodies and would support both body weight normalized dosing or a fixed dose across all body weights.

The choice of the 200 mg Q3W as an appropriate dose for the switch to fixed dosing is based on simulations performed using the population PK model of pembrolizumab showing that the fixed dose of 200 mg every 3 weeks will provide exposures that 1) are optimally consistent with those obtained with the 2 mg/kg dose every 3 weeks, 2) will maintain individual patient exposures in the exposure range established in melanoma as associated with maximal efficacy response and 3) will maintain individual patients exposure in the exposure range established in melanoma that are well tolerated and safe. A fixed dose regimen will simplify the dosing regimen to be more convenient for physicians and to reduce potential for dosing errors. A fixed dosing scheme will also reduce complexity in the logistical chain at treatment facilities and reduce wastage.

### 5.1.2 Definition of dose-limiting toxicity

A DLT is defined as any toxicity not attributable to the disease or disease-related processes under investigation, which occurs from the start of combination ( post dose Day 1 Cycle 1) up to 42 days and is considered by the Investigator to be definitely, probably, or possibly related to the treatment. A DLT will be defined as any Grade 3 or higher treatment-related toxicity that occurs during the DLT evaluation period, including:

1. Any Grade 4 immune-related AE (irAE) irrespective of duration
2. Any Grade 3 or 4 non-infectious pneumonitis irrespective of duration
3. Any Grade 3 irAE, excluding colitis or pneumonitis, that does not downgrade to Grade  $\leq 2$  within 3 days after onset despite maximal supportive care including systemic corticosteroids or downgrade to Grade  $\leq 1$  within 14 days after onset of the event.
4. Any  $\geq$  Grade 2 pneumonitis or interstitial lung disease (ILD) that does not resolve to grade 1 within 3 days of the initiation of maximal supportive care
5. Liver transaminase elevation higher than  $10 \times$  upper limit of normal (ULN) or total bilirubin higher than  $5 \times$  ULN **that lasts for longer than 7 days**. Any grade 3-4 non hematologic toxicity which does not resolve within 4 days will be considered a DLT.

**A DLT excludes the following conditions:**

1. Vitiligo or alopecia of any grade.
2. Isolated laboratory changes of any grade without clinical sequelae or clinical significance.
3. Grade 3 endocrinopathy that is managed with or without systemic corticosteroid therapy and/or hormone replacement therapy and the subject is asymptomatic
4. Grade 3 inflammatory reaction attributed to a local antitumor response (e.g., inflammatory reaction at sites of metastatic disease, lymph nodes, etc.) that resolves to  $\leq$  Grade 1 within 30 days. Immune-related adverse events are defined as AEs of immune nature (i.e., inflammatory) in the absence of a clear alternative etiology. In the absence of clinical abnormality, repeat laboratory testing will be conducted to confirm significant laboratory findings prior to designation as a DLT. However isolated laboratory changes of any grade without clinical sequelae or clinical significance are not considered DLTs.

### 5.1.3 Definition of maximum tolerated dose

A dose will be considered non-tolerated and dose escalation will cease if 2 or more of up to 6 evaluable subjects experience a DLT at a dose level. Once the non-tolerated dose is defined the MTD will be confirmed at the previous dose-level below the non-tolerated dose or a dose between the non-tolerated dose and the last tolerated dose may be investigated. Six evaluable subjects are required to determine the MTD.

#### **5.1.4 Definition of evaluable subject**

For decisions on dose escalation, an evaluable subject is defined as a subject that meets all of the following criteria:

- Has received ibrutinib at the protocol-specified dose for at least 36 out of first 42 days of combination therapy
- Has received one infusion of pembrolizumab at the protocol-specified full dose during the first 42 days of therapy
- Has completed the minimum safety evaluation requirement which is defined as the time from consent to 42 days after the first dose.

OR

- Has experienced a DLT any time during the first 42 days of combination therapy.

#### **5.1.5 Dose Modifications for Treatment-Related Toxicity**

All toxicities will be graded according to National Cancer Institute's (NCI's) Common Terminology Criteria for Adverse Events (CTCAE) (NCI CTCAE v 4.03).

##### **Phase I:**

No dose modifications will be allowed in the escalation phase during the DLT evaluation period.

If a subject experiences a clinically significant and/or unacceptable toxicity including a DLT not attributable to the disease or disease-related processes under investigation, dosing will be interrupted and supportive therapy administered as required.

##### **Phase II:**

Dose reductions for AEs related to ibrutinib will be performed as per Table 1 below.

Dose modifications will not be required for AEs that are clearly not attributed to ibrutinib or pembrolizumab (such as an accident) or for laboratory abnormalities that are not deemed to be clinically significant.

Dosing may continue despite concurrent vitiligo of any AE grade.

If a subject experiences a clinically significant and/or unacceptable toxicity, dosing will be interrupted and supportive therapy administered as required.

### 5.1.6 Dose Delays for Treatment-Related Toxicity

Toxicity that occurs during the expansion phase should be classified as drug related or non-drug related. Attribution of toxicity is at the discretion of the principal investigator. The study investigator will determine if either or both medications should be held.

**Table 1: Criteria for Dose Delays in Case of Suspected Ibrutinib Toxicity**

Non-hematologic toxicity	Actions

Grade 3 or greater
	
 
• Interrupt ibrutinib until recovery to grade <math>\leq 1</math>.
 
• Then reintroduce ibrutinib at same dose.
 
• If the toxicity reoccurs, reduce dose by one capsule
 
• A second dose reduction of 140 mg may be considered if needed
 
• If toxicity remains despite two dose reductions, discontinue ibrutinib
 

Hematologic toxicity	
Actions
 
Note: Growth factors, including platelets and GCSF, will not be administered prophylactically but may be prescribed at the discretion of the treating physician

Grade 4
	
 
• Interrupt ibrutinib until recovery to grade <math>\leq 1</math>.
 
• Then reintroduce ibrutinib at same dose.
 
• If the toxicity reoccurs, reduce dose by one capsule
 
• A second dose reduction of 140 mg may be considered if needed
 
• If toxicity remains despite two dose reductions, discontinue ibrutinib
 

Grade <math>\geq 3</math> Neutropenia (neutrophils <math>< 1,000/\text{mm}^3</math>, <math>\geq 500/\text{mm}^3</math>) with infection or fever
	
 
• Interrupt ibrutinib until recovery to grade <math>\leq 1</math>.
 
• Then reintroduce ibrutinib at same dose.
 
• If the toxicity reoccurs, reduce dose by one capsule
 
• A second dose reduction of 140 mg may be considered if needed
 
• If toxicity remains despite two dose reductions, discontinue ibrutinib
 

**Table 2: Criteria for Dose Delays in Case of Suspected Pembrolizumab Toxicity**

Toxicity	Hold Treatment For Grade	Timing for Restarting Treatment	Treatment Discontinuation
Diarrhea/Colitis	2-3	Toxicity resolves to Grade 0-1	Toxicity does not resolve within 12 weeks of last dose or inability to reduce corticosteroid to 10 mg or less of prednisone or equivalent per day within 12 weeks
	4	Permanently discontinue	Permanently discontinue
AST, ALT, or Increased Bilirubin	2	Toxicity resolves to Grade 0-1	Toxicity does not resolve within 12 weeks of last dose
	3-4	Permanently discontinue (see exception below) a	Permanently discontinue
Type 1 diabetes mellitus (if new onset) or Hyperglycemia	T1DM or 3-4	Hold pembrolizumab for new onset Type 1 diabetes mellitus or Grade 3-4 hyperglycemia associated with evidence of beta cell failure	Resume pembrolizumab when patients are clinically and metabolically stable
Hypophysitis	2-4	Toxicity resolves to Grade 0-1. Therapy with pembrolizumab can be continued while endocrine replacement therapy is instituted	Toxicity does not resolve within 12 weeks of last dose or inability to reduce corticosteroid to 10 mg or less of prednisone or equivalent per day within 12 weeks
Hyperthyroidism	3	Toxicity resolves to Grade 0-1	Toxicity does not resolve within 12 weeks of last dose or inability to reduce corticosteroid to 10 mg or less of prednisone or equivalent per day within 12 weeks
	4	Permanently discontinue	Permanently discontinue
Hypothyroidism		Therapy with pembrolizumab can be continued while thyroid replacement therapy is instituted	Therapy with pembrolizumab can be continued while thyroid replacement therapy is instituted
Infusion Reaction	2 b	Toxicity resolves to Grade 0-1	Permanently discontinue if toxicity develops despite adequate premedication
	3-4	Permanently discontinue	Permanently discontinue
Pneumonitis	2	Toxicity resolves to Grade 0-1	Toxicity does not resolve within 12 weeks of last dose or inability to reduce corticosteroid to 10 mg or less of prednisone or equivalent per day within 12 weeks
	3-4	Permanently discontinue	Permanently discontinue
Renal Failure or Nephritis	2	Toxicity resolves to Grade 0-1	Toxicity does not resolve within 12 weeks of last dose or inability to reduce corticosteroid to 10 mg or less of prednisone or equivalent per day within 12 weeks
	3-4	Permanently discontinue	Permanently discontinue
All Other Drug-Related Toxicity c	3 or Severe	Toxicity resolves to Grade 0-1	Toxicity does not resolve within 12 weeks of last dose or inability to reduce corticosteroid to 10 mg or less of prednisone or equivalent per day within 12 weeks
	4	Permanently discontinue	Permanently discontinue

**Note: Permanently discontinue for any severe or Grade 3 drug-related AE that recurs or any life-threatening event.**

a For patients with liver metastasis who begin treatment with Grade 2 AST or ALT, if AST or ALT increases by greater than or equal to 50% relative to baseline and lasts for at least 1 week then patients should be discontinued.

b If symptoms resolve within one hour of stopping drug infusion, the infusion may be restarted at 50% of the original infusion rate (e.g., from 100 mL/hr to 50 mL/hr). Otherwise dosing will be held until symptoms resolve and the subject should be premedicated for the next scheduled dose; Infusion Treatment Guidelines for further management details.

c Patients with intolerable or persistent Grade 2 drug-related AE may hold study medication at physician discretion. Permanently discontinue study drug for persistent Grade 2 adverse reactions for which treatment with study drug has been held, that do not recover to Grade 0-1 within 12 weeks of the last dose.

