#### 4. Eligibility

##### 4.1 Inclusion Criteria

- Histologically confirmed diagnosis of colorectal adenocarcinoma
- Measurable or non-measurable disease by Response Evaluation Criteria in Solid Tumors (RECIST) 1.1. Stage IV or recurrent disease is required.
- Patients must have received and progressed through or become intolerant to fluoropyrimidine, irinotecan, oxaliplatin, and bevacizumab. If RAS wild type, patients should have received and progressed or become intolerant to the above as well as cetuximab or panitumumab containing therapies. Prior therapy with Regorafenib and/or TAS 102 is allowed
- ECOG Performance Score 0 or 1
- Estimated life expectancy > 3 months
- Adequate bone marrow, liver and renal function as assessed by the following:
  - o Hemoglobin > 8.0 g/dl
  - o Absolute neutrophil count (ANC) > 1,000/mm^3 independent of growth factor support
  - o Platelet count > 100,000/mm^3
  - o Total bilirubin < 1.5 times ULN unless bilirubin rise is due to Gilbert's syndrome or of non-hepatic origin
  - o AST, ALT and Alkaline Phosphatase ≤2.5 times the ULN (≤5 x ULN for patients with liver involvement)
  - o Creatinine clearance ≥ 30 ml/min
- Patients must not have had chemotherapy, major surgery, monoclonal antibody therapy or experimental therapy within the 21 days prior to the start of ibrutinib administration
- Women of childbearing potential must have a negative serum or urine pregnancy test performed within 7 days prior to the start of study drug. Post-menopausal women (defined as no menses for at least 1 year) and surgically sterilized women are not required to undergo a pregnancy test.
- Subjects (men and women) of childbearing potential must agree to use adequate contraception beginning at the signing of the ICF until at least 4 months for both females and males after the last dose of study drug. The definition of adequate contraception will be based on the judgment of the principal investigator or a designated associate.
- Subjects (men and women) must agree to not donate sperm (males) or eggs (females) during and up to 120 days after the last dose of study treatment.
- Subjects must be able to understand and be willing to sign the written informed consent form. A signed informed consent form must be appropriately obtained prior to the conduct of any trial-specific procedure. Subjects must be willing and able to comply with scheduled visits, treatment schedule, laboratory testing, and other study requirements.

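### Table 2's Grade 2 liver row has no baseline exception for patients admitted with Grade 2 AST/ALT: once held, they can restart pembrolizumab only below their own entry value, and footnote a conflicts with the row

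*Combined protocol and SAP*

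**What the plan says.** **Entry.** Section 4.1 sets the limit as "AST, ALT and Alkaline Phosphatase ≤2.5 times the ULN (≤5 x ULN for patients with liver involvement"). Section 4.2 excludes unresolved toxicity above Grade 1 only where it comes from earlier therapy or a procedure, so Grade 2 values caused by liver metastases are not excluded.

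**Table 2 (section 5.1.6), row "AST, ALT, or Increased Bilirubin".**
- Grade 2: hold pembrolizumab. The restart column reads "Toxicity resolves to Grade 0-1" and the discontinuation column reads "Toxicity does not resolve within 12 weeks of last dose". Neither mentions baseline.
- Grades 3-4: the restart column reads "Permanently discontinue (see exception below"), with the marker for footnote a. The discontinuation column next to it calls for permanent discontinuation and carries no marker.

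**Footnote a.** It is worded for a population, "For patients with liver metastasis who begin treatment with Grade 2 AST or ALT". It discontinues them if AST or ALT rises by 50% or more over baseline for at least a week. It names no on-treatment grade, and does not say what happens below that threshold.

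**Section 5.5.6.** Grade 2 hepatic events get closer monitoring until values are back at baseline. The steroid taper in the same section starts at Grade 1 or less.

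**Table 1 (ibrutinib).** There is no liver row. For non-hematologic toxicity of Grade 3 or greater it says "Interrupt ibrutinib until recovery to grade" 1 or lower, again without reference to baseline.

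**The concern.** The protocol deliberately admits patients whose AST/ALT is already Grade 2, and footnote a shows that its authors had them in mind. The Grade 2 row nevertheless treats everyone as if they had started at Grade 0-1. For a patient admitted at Grade 2 and then held, getting back to the entry value is not enough to restart, and after 12 weeks the drug is stopped for good. Section 5.5.6 uses return to baseline as its monitoring target for the same events.

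Two things are at stake. A patient could lose pembrolizumab permanently with liver values no worse than at enrolment. And where footnote and row overlap, the text gives two answers or none, so different investigators could handle the same patient differently, each with support in the protocol.

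**Working it through.** The plan states no figure on this point, so there is none to reproduce. The check compares the thresholds.

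**Inputs from the protocol:** entry cap 5 x ULN with liver involvement (4.1); hold at Grade 2, restart at Grade 0-1, 12-week limit from last dose (Table 2); rise of at least 50% over baseline for at least a week (footnote a).

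**Assumptions:** the protocol does not print the grade cut-offs. I take Grade 2 to end at 5 x ULN and to start at L, between 2.5 and 3.0 x ULN.

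**1. Where the restart criterion lies.** The fall below baseline b needed to leave Grade 2 is (b - L)/b.
- b = 4: (4 - 3.0)/4 = 25%, to (4 - 2.5)/4 = 37.5%.
- b = 5: (5 - 3.0)/5 = 40%, to (5 - 2.5)/5 = 50%.

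For any b within Grade 2 the result is positive, so restart always requires a value better than at entry.

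**2. Where footnote a meets the Grade 2 row.** The footnote's trigger is 1.5 x b. It stays within Grade 2 when 1.5 x b is at most 5, that is, b up to 5/1.5 = 3.33 x ULN.

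**3. Four cases side by side**, each a rise suspected to be due to pembrolizumab and judged clinically significant, sustained for at least a week:

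| Baseline to on-treatment (x ULN) | Rise | Assumed grade | Table 2 row | Footnote a, as worded |
|---|---|---|---|---|
| 3.2 to 4.8 | 4.8/3.2 = 1.50 | 2 | Hold; restart at Grade 0-1 | Discontinue |
| 4.0 to 4.8 | 4.8/4.0 = 1.20 | 2 | Hold; restart at Grade 0-1; stop at 12 weeks if unresolved | Threshold not met |
| 4.0 to 5.8 | 5.8/4.0 = 1.45 | 3 | Restart cell: discontinue, subject to the exception. Next cell: discontinue, no exception | Threshold not met; hold and restart not stated |
| 4.0 to 6.0 | 6.0/4.0 = 1.50 | 3 | Discontinue | Discontinue |

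Only the last case has row and footnote agreeing on one outcome. The first has two. The second has one under the row, but with a restart criterion the patient did not meet at entry. The third has none that the text settles.

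**4. Timing of the 12-week limit.** 12 weeks is 84 days, or four 3-week cycles, counted from the last dose. Four months is about 122 days. With infusions on days 1, 22 and 43, the limit falls on day 1 + 84 = 85, 22 + 84 = 106 or 43 + 84 = 127. A permanent stop under this rule therefore precedes the 4-month assessment only if the last infusion was the first or second. The hold itself begins earlier.

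**The case against.** **A hold does not follow from the entry value alone.** A reader might infer that a patient admitted at Grade 2 meets the hold condition on day 1. The documents do not support that. Table 2 concerns suspected pembrolizumab toxicity. Section 8.1.1 counts a pre-existing condition as an adverse event only if it worsens. For phase II, section 5.1.5 requires no modification for laboratory changes not considered clinically significant, and section 5.1.6 leaves attribution to the principal investigator. This stands and narrows the point to worsening that is suspected to be drug-related and clinically significant. It does not remove the point: these clauses govern whether a hold starts, not what ends it. The significance clause is also partly circular, because section 8.1.1 defines clinically significant results to include those requiring a change of treatment.

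**Footnote a may be meant as the complete rule for this group.** Its wording is by population and can reach Grade 2 values. This reading is open, and it is why one cannot state as fact that a larger rise is handled more leniently than a smaller one. The footnote also does not say that a patient below its threshold continues, and the unmarked Grade 3-4 discontinuation cell points the other way. But its marker sits only on the Grade 3-4 restart cell, and it contains no hold or restart rule. That the reading is open shows the text needs settling.

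**Table 1.** It would be wrong to say that both dose-change tables have a defective liver row. Table 1 has none. It shares only the recovery-to-Grade-1 condition, and only after an event of Grade 3 or greater.

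**Conclusion.** The inconsistency is in the current text. For patients admitted with Grade 2 AST/ALT, Table 2's Grade 2 row makes restart depend on a value below their own baseline. Footnote a, the only baseline-relative dosing rule, is attached to a different cell and conflicts with the row for baselines up to about 3.33 x ULN. A smaller rise that reaches Grade 3 has no single stated outcome, and section 5.5.6 monitors to a different target. The cut-offs used (Grade 2 starting at 2.5-3.0 and ending at 5 x ULN) are assumptions. The finding that the restart criterion lies below baseline does not depend on their exact values.

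A reader might go on to infer that this could decide the trial, since success requires 4 of 32 patients with disease control. The documents do not support that. They give neither the share entering at Grade 2 nor the share of those who would have a qualifying rise that fails to reach Grade 1. A patient off pembrolizumab can still count as having disease control at 4 months: ibrutinib need not be held at the same time (5.1.6), and patients who discontinue stay in follow-up (4.3). The number affected and the effect on the endpoint are therefore unknown. The point is a contradiction in treatment rules that should be corrected, not a demonstrated bias in the primary analysis.

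**What to change.** Reconcile the AST/ALT limit in section 4.1, the Grade 2 and Grade 3-4 liver rows of Table 2 (including the unmarked discontinuation cell), footnote a and where it is marked, the recovery line in Table 1, and section 5.5.6. After reconciliation, hold, restart and discontinuation should each give one outcome for a patient admitted with Grade 2 AST/ALT, whether a rise stays within Grade 2 or goes beyond it. Which outcome applies is a clinical decision for the sponsor, and none is proposed here.

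The cost is a wording amendment to these passages. It needs no added procedures, visits or patients, and leaves the design and sample size as they are.
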